## 3 DATA ANALYSIS CONSIDERATIONS

### 3.1 General presentation of summaries and analyses

Statistical evaluation will be performed by PAREXEL and supervised by the Exploratory Statistics and Global Statistical Sciences Departments of UCB.

The datasets will follow the UCB analysis data model data specifications.

All analyses will be performed using SAS version 9.2 or higher (SAS Institute, Cary, North Carolina, USA). R Version 2.10.1 (R Development Core Team) or later, and/or OpenBUGS Version 3.0.6 or later may be used for complementary analysis.

Descriptive statistics will be used to provide an overview of the Baseline, efficacy, PD, PK and safety results. Formal statistical testing will be conducted for the primary and secondary efficacy variables only in this study. Other efficacy variables will be summarized descriptively by treatment group.

Continuous variables will be summarized by treatment, visit and time point (where applicable) including number of subjects (n), mean, SD, median, minimum and maximum. First and third quartiles (Q1 and Q3 respectively) and 95% confidence intervals (CI) for the mean will also be included where stated in the SAP.

Categorical variables will be summarized by treatment, visit and time point (where applicable) with frequency counts and percentages. Geometric coefficient of variation (geoCV), geometric mean and 95% CI for the geometric mean will also be presented in the descriptive statistics for the PK concentration and hs-CRP data. In all outputs the 95% confidence limits will be restricted to the possible values that the variable can take.

When reporting relative frequencies or other percentage values, the following rules apply:

- For values where all subjects fulfill certain criteria, the percentage value will be displayed as 100
- For values where the absolute frequency is zero, there will be no percentage displayed at all
- All other percentage displays will use 1 decimal place
- Unless otherwise stated, the denominator for the percentages will be based on the number of subjects in the respective analysis set and treatment group.

Percentages displayed based on continuous data (eg, percentage changes from Baseline) will be displayed to 1 decimal place.

When reporting descriptive statistics, the following rules will apply in general (with the exception of PK and hs-CRP data, for which additional rules are stated below):

- n will be an integer

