### 3.5.8 PET Per-Protocol Set

The PET Per-Protocol Set (PET-PPS) will consist of all randomized subjects who receive at least 1 dose of the IMP and have evaluable PET-MRI or PET-CT scan data at Baseline and at least 1 of the post-Baseline assessments.

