Another reader who has not been involved in the visual identification of the PET-positive lesions, either as a primary reader or an adjudicator, will then draw volumes of interest (VOIs) on the pre-identified PET-positive lesions. In the case that no PET-positive lesions have been identified for a subject, then the final review step to draw VOIs will not occur. Efficacy PET-MRI/PET-CT review will occur provided that an acceptable PET-CT or PET-MRI scan is available and that PET-positive lesions were identified on the previous scan (for the Week 12 and Week 48 visits). During the PET-positive lesion VOI review, the independent reviewer will perform a quantitative assessment in ACCURATE and record the standard uptake values of  $^{18}\text{F}$ -fluoride in VOIs, corrected for both body weight and individual integrated whole blood activity concentration (SUVauc) for each PET-positive lesion identified during the PET-positive lesion identification review.

Data from the visual identification of PET-positive lesions and the results of the quantitative VOI review (i.e. SUVauc) will be listed, for each independent reader and adjudicator (if applicable), for each anatomical location in the spine, and for each side of the SIJ, by treatment group and visit for subjects in the SS who were enrolled into the PET-MRI/PET-CT substudy.

No formal statistical modelling of the PET-MRI/PET-CT imaging data will be performed for this substudy; only summaries will be presented together with 95% CIs for mean values, as applicable.

The summaries described below based on the visual identification of PET-positive lesions will include the final assessment data, ie, if adjudication was performed, then the adjudicated data will be summarized, otherwise data from one of the primary reviewers will be summarized.

All summaries will be presented for the PET-PPS.

Since the attenuation correction and quantification is variable in PET-MRI scans, PET-MRI imaging data will be listed but will not be aggregated with the PET-CT imaging data in the summaries.

Due to the predicted sparseness of the number of PET-positive lesions in each of the individual anatomical locations of the spine, data will be pooled as follows for the purpose of some of the summaries:

- In the SIJ and spine overall (across the SIJ and all anatomical locations in the spine);
- In the SIJ overall (across both sides), and split by Left and Right side;

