- In the spine overall (across all anatomical locations in the spine), and split by spinal regional level (Cervical, Thoracic, Lumbar, Sacrum), and, depending on the distribution of lesions across the spine, further by spinal levels and spinal locations in which at least 1 PET-positive lesion is identified.

An overview of the total number of PET-positive lesions identified in the spine across all subjects in each of the individual anatomical locations will be presented by visit.

The presence of PET-positive lesions identified in the SIJ and spine will be summarized by visit. The summary will include the number and percentage of subjects at each visit with any PET-positive lesions in the spine or the SIJ, in both the spine and the SIJ, in the SIJ overall (and split by Left and Right side) and in the spine overall [and split by spinal regional level (Cervical, Thoracic, Lumbar and Sacrum) and level/location, as applicable]. This summary will also

include a total count of PET-positive lesions across subjects for each of the pooled locations described above. In the spine, the incidence and the total number of lesions will only be presented for the anatomical locations in which at least 1 PET-positive lesion is identified.

The number of PET-positive lesions per subject in the SIJ and spine (overall and in pooled locations, as described above) will be calculated and summarized by visit using frequency counts and percentages, and/or descriptive statistics, as applicable. In addition, in the spine and SIJ overall, in the spine overall and in each spinal regional level, the changes in the number of PET-positive lesions per subject from Baseline to Week 12 and Week 48, and the changes from Week 12 to Week 48 will be summarized using descriptive statistics.

Bar charts summarizing the total number of PET-positive lesions identified in the SIJ and in the spine will be presented by treatment group and visit for each of the pooled locations described above.

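### Read literally, the SAP keeps PET-MRI subjects in the denominator of the PET lesion percentages but never in the numerator

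*SAP*

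**What the plan says.** Four statements in the SAP bear on this.

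- **Membership (3.5.8).** Subjects enter the PET-PPS if they are randomized, have received at least one dose and "have evaluable PET-MRI or PET-CT scan data at Baseline and at least 1 of the post-Baseline assessments". Either modality qualifies.
- **Set used (8.3.6.2).** "All summaries will be presented for the PET-PPS".
- **Handling of PET-MRI (8.3.6.2, the next paragraph).** "PET-MRI imaging data will be listed but will not be aggregated with the PET-CT imaging data in the summaries". The reason given is technical: "Since the attenuation correction and quantification is variable in PET-MRI scans".
- **Default denominator (3.1).** "Unless otherwise stated, the denominator for the percentages will be based on the number of subjects in the respective analysis set and treatment group".

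The percentages at issue are also in 8.3.6.2: "The summary will include the number and percentage of subjects at each visit with any PET-positive lesions in the spine or the SIJ", with further rows for the SIJ, the spine and the spinal regions. The number of lesions per subject may be tabulated as frequencies and percentages as well. Neither description names a denominator.

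Elsewhere the SAP does override the default. The vital signs (11.4.1) and ECG (11.4.2) sections use subjects who have a value at the visit, and the immunology section (10) uses the observations at each visit.

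**The concern.** The rules for who is in the set, which data are summarized and what percentages are divided by do not fit together. PET-MRI subjects belong to the set that supplies the denominator, but their scans are kept out of the tables that supply the numerator. A programmer who follows the text as it stands would divide PET-CT positives by PET-CT plus PET-MRI subjects.

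This matters because no formal modelling of the imaging data is planned, so descriptive tables are the main output of the substudy. Protocol Amendment 3 and SAP 2.4 raise the total to at least 72 subjects in order to secure at least 25 evaluable imaging subjects and to show broad differences between the arms. The documents describe no stratification of the randomization by scanner type. A difference between the arms in scanner mix would therefore appear in the tables as a difference in lesion frequency.

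**Working it through.** The documents state no lesion percentage, PET-MRI count or PET power, so there is no planned figure to reproduce. The check is an identity evaluated over an assumed range.

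**Inputs**
- Substudy size: at least 25 (Protocol 15.12; SAP 2.4). N = 25 is used.
- Allocation: 2:1 (Protocol 15.12). Arms of 17 bimekizumab and 8 CZP are assumed; the documents give no allocation for the substudy itself.
- PET-MRI subjects in the PET-PPS, k: not given. A range of 0 to 10 is assumed.
- True percentage among PET-CT subjects, p: not given, except that Baseline can be inferred (step 2).

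**1. Dilution.** Printed percentage = p × (N - k)/N = p × (1 - m), with m = k/N. The relative reduction is m. The loss in percentage points is p × m, which equals m only when p = 100%. With k = 5, m = 5/25 = 20%:

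| True p | Printed | Points lost |
|---|---|---|
| 50% | 40% | 10 |
| 80% | 64% | 16 |
| 100% | 80% | 20 |

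With k = 0 the printed and true values agree.

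**2. Baseline as an internal check.** The PET-PPS requires evaluable post-Baseline scan data, and a Week 12 or Week 48 scan is done and reviewed only if the previous scan showed lesions (Protocol Table 5-1, footnote o; SAP 8.3.6.2). Essentially every PET-PPS subject is therefore PET-positive at Baseline, and the true figure for any lesion is about 100%. Printed value = 100 × (25 - k)/25:

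| k | 0 | 3 | 5 | 7 | 10 |
|---|---|---|---|---|---|
| Printed | 100% | 88% | 80% | 72% | 60% |

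**3. Contrast between arms.** The factor applies arm by arm. With p = 80% in both arms:

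| PET-MRI in bimekizumab, CZP | Bimekizumab | CZP |
|---|---|---|
| 2, 1 | 80 × 15/17 = 70.6% | 80 × 7/8 = 70.0% |
| 3, 3 | 80 × 14/17 = 65.9% | 80 × 5/8 = 50.0% |
| 1, 4 | 80 × 16/17 = 75.3% | 80 × 4/8 = 40.0% |

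A near-proportionate split causes almost no contrast. The last row is an unlikely split: with 5 PET-MRI subjects allocated at random its probability is C(8,4) × C(17,1)/C(25,5) = 70 × 17/53,130 = 0.02.

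For Baseline, with a true 100% in both arms and k split at random (hypergeometric: 25 subjects, 8 of them CZP), the printed percentages differ between arms as follows:

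| k | 3 | 5 | 7 | 10 |
|---|---|---|---|---|
| P(at least 10 points) | 0.53 | 0.64 | 0.64 | 0.67 |
| P(at least 20 points) | 0.02 | 0.28 | 0.36 | 0.40 |

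One CZP subject is worth 100/8 = 12.5 points, so the 10-point row mostly reflects how small the arm is. The 20-point row is the more telling one.

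**4. What is not touched.** SUVauc means, changes and percentage changes are computed from observed values, and total lesion counts have no denominator. None of these is scaled by (1 - m).

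**The case against.** The strongest reply is that the PET denominator is inferred. It comes from a default that yields to any statement to the contrary. The sentence on PET-MRI directly follows the one naming the PET-PPS, and can be read as making the tables PET-CT only, with N to match. Protocol 15.2 points the same way, since it bases denominators on the subjects suited to the purpose of the analysis. This may well be the intent. What stands against it is that SAP 3.1 is more specific than the protocol, that the SAP writes out its other departures from the default, and that nothing restricts the PET-PPS or its N to PET-CT.

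Three further points are fair. The number of PET-MRI subjects is unknown and may be zero. The error would be recoverable, because counts are shown beside percentages, PET-MRI data are listed, and a Baseline figure well below 100% should prompt a question. The consequence is also limited: the PET analysis is exploratory and unpowered, its protocol variable is SUVauc, and no success criterion uses these percentages. These points reduce the weight of the issue without reconciling the three rules.

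A reader might infer more: that every PET percentage is certainly too low, or is too low by the PET-MRI share in percentage points. The documents support neither. The first needs at least one PET-MRI subject in the set and the literal denominator. The second confuses a relative reduction within each arm with an absolute one.

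**Conclusion.** The point holds conditionally. Taken literally, SAP 3.1, 3.5.8 and 8.3.6.2 give a numerator and a denominator that do not match for the lesion-presence percentages, and for the lesion-count percentages where these are produced. Each arm's figure is multiplied by (1 - m) for that arm. The size depends on a share that the documents do not state: nothing at 0 of 25, and a Baseline 100% printed as 60% at 10 of 25. The between-arm figures rest additionally on the assumed 17:8 split and on random allocation of scanner type.

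It would be wrong to extend this to the SUVauc results or lesion totals, or to treat it as a threat to the primary analysis. It is a contradiction in the tabulation rules of an exploratory substudy. It is still worth correcting, because no model will correct these tables afterwards and the correction is small.

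**What to change.** In SAP 8.3.6.2, add that percentages in the PET summaries use as denominator the PET-PPS subjects in the arm with an evaluable PET-CT scan at that visit. Show that n by arm and visit, and report the number of PET-MRI subjects per arm.

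The denominator has to be set by visit. Using all PET-CT subjects in the arm would still count, at Weeks 12 and 48, those who were not rescanned because the previous scan was negative or because they had withdrawn. A footnote should say that follow-up percentages therefore describe rescanned subjects only.

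The section should also say whether visual lesion presence from PET-MRI is meant to be excluded, since the stated reason concerns attenuation correction and quantification only. If it is to be shown, it needs its own denominator.

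The cost is one sentence in the SAP, one subset condition in the programs, and a smaller stated N in the PET tables.

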5.3 Imaging evaluation

In a subpopulation of AS0013, a PET-MRI or PET-CT scan of the entire spine will be performed at selected sites in approximately 25 subjects at Screening, and during the study at Week 12 and Week 48/Early Withdrawal Visit if PET-positive lesions were observed in the previous scan.

The PET-MRI or PET-CT scan should be performed after confirmation of eligibility for the study based on screening assessments. All subjects at selected sites are eligible provided that a separate Informed Consent form (ICF) for the imaging evaluation has been signed.

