## 2.3 Study design and conduct

AS0013 is a multicenter, randomized, subject-blind and investigator-blind, parallel-group study to evaluate the efficacy and safety of BKZ compared to CZP in adult subjects with active adult-onset AS.

It is planned that at least 60 subjects will be randomized to 1 of 2 treatment arms in a 2:1 ratio and will receive either BKZ or CZP up to Week 44 (final dose of investigational medicinal product [IMP]).

The study will include a Screening Period of 2 to 4 weeks, a 12-week Treatment Period, a 36-week Treatment Extension Period, and a 20-week Safety Follow-up (SFU) Period (starting after the final dose of IMP). Therefore, the maximum duration of the study will be 68 weeks.

At the start of the Treatment Period, eligible subjects will be randomized in a 2:1 ratio to receive the following blinded study treatments:

- BKZ 160mg sc Q2W from Week 0 through Week 10. In addition, subjects will receive 1 placebo injection at Baseline (Visit 2), Week 2 (Visit 3), and Week 4 (Visit 3) in order to maintain the blind versus the CZP loading dose at these visits.
- CZP 400mg sc Q2W at Weeks 0, 2, and 4 (loading dose) followed by CZP 200mg sc Q2W at Weeks 6 to 10.

After completing the 12-week Treatment Period, subjects will enter a 36-week Treatment Extension Period and will receive the following treatments:

- Subjects randomized to BKZ during the Treatment Period will receive BKZ 320mg sc every 4 weeks (Q4W) from Week 12 to Week 44.
- Subjects randomized to CZP during the Treatment Period will receive CZP 400mg Q4W from Week 12 to Week 44.

Subjects not responding to treatment during the Treatment Period will be withdrawn from the study as per Investigator's discretion and will not enter the Treatment Extension Period.

In a substudy of AS0013, a PET-MRI or PET-CT scan of the entire spine will be performed at selected sites in approximately 25 subjects at Screening and during the study at Week 12 and Week 48 or Early Withdrawal Visit if PET positive lesions were observed in the previous scan.

All subjects who complete the study or who discontinue from the study early, including those withdrawn from the IMP treatment, will have a SFU Visit at 20 weeks after their final dose of IMP.

Three unblinded interim analyses will be conducted:

- Interim Analysis 1 (IA1): when approximately 45 subjects have completed the Week 4 visit during the Treatment Period.

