## 2.4 Determination of sample size

A sufficient number of subjects will be enrolled to ensure that at least 60 subjects are available in the main study at Week 12 to compare the change from Baseline in ASDAS between BKZ and CZP. This will also provide at least 25 subjects enrolled in the PET-CT or PET-MRI substudy from multiple sites. Subjects will be randomized in a 2:1 ratio to receive BKZ or CZP respectively.

The sample size was calculated to provide at least 80% power to detect a difference between treatment groups in the mean change from Baseline in ASDAS at Week 12 of 0.89 (group mean change from Baseline for CZP and BKZ being -1.78 and -2.67 respectively) with a common standard deviation (SD) of 1.17 using frequentist methods for the comparison of the treatment group mean change from Baseline in ASDAS at Week 12 with Baseline ASDAS as a covariate (Overall and Starbuck, 1979).

The correlation between Baseline and Week 12 raw ASDAS was assumed to be 0.35. Note that the informative prior for the model intercept to be used in the Bayesian modelling of the primary efficacy variable, given by  $\beta_{CZP} \sim \text{Normal}(-1.78, \text{var}=0.0605)$ , contributes an effective sample size of approximately 20 CZP subjects. Prior data conflict will be investigated, and a vague prior will be used for the model intercept coefficient if prior data conflict is evident.

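### The lesion bar charts plot arm totals in a 2:1 trial, so equal arms would look about two-fold different, and withdrawals would lower the Week 48 bars with no lesion resolved

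*SAP*

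**What the plan says.** SAP 8.3.6.2 (Efficacy assessment) plans "Bar charts summarizing the total number of PET-positive lesions identified in the SIJ and in the spine", shown by treatment group and visit. This is to be done for each pooled location. Neither a per-subject nor a per-scan denominator is mentioned. On allocation, SAP 2.4 says: "Subjects will be randomized in a 2:1 ratio to receive BKZ or CZP respectively". The same section expects "at least 25 subjects enrolled in the PET-CT or PET-MRI substudy from multiple sites".

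Other rules decide which subjects stand behind each bar:

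- **Follow-up scans.** Protocol 5.3 schedules the Week 12 and Week 48 scans only "if PET-positive lesions were observed in the previous scan". SAP 8.3.6.2 applies the same condition to the image review.
- **Withdrawal scans.** Protocol Table 5-1, footnote o, asks for a scan at the withdrawal visit only when the last one is more than 12 weeks old and was positive.
- **Withdrawal data.** Under SAP 4.4, early-withdrawal results that map to a visit where the assessment is not scheduled are listed but not summarized. PET is scheduled only at Screening, Week 12 and Week 48.
- **Non-responders.** SAP 2.3 lets the investigator withdraw Week 12 non-responders, who then do not enter the extension.
- **Analysis set.** PET summaries use the PET-PPS (SAP 3.5.8), which needs evaluable scan data at Baseline and at one or more later assessments.
- **Modality.** PET-MRI results are listed but not combined with PET-CT results in the summaries (SAP 8.3.6.2).

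SAP 8.3.6.2 also plans the percentage of subjects with lesions, the number of lesions per subject, and per-subject changes between visits.

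**The concern.** A total is the product of lesion burden and the number of subjects scanned. Here the number scanned differs between arms by design and can fall over time through withdrawal. A reader comparing the two arms at one visit sees arm size mixed with burden. A reader following one arm from Baseline to Week 48 sees loss of subjects mixed with resolution of lesions.

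The substudy has no formal modelling and is meant to show broad differences between the arms, so its displays matter. The other PET figures in SAP 8.3.6.2 (spaghetti plots, waterfall plots, mean plots) all show uptake values. These bars are the only planned figure of lesion counts.

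**Working it through.** The plan gives no figure of its own to reproduce here: SAP 2.4 says that power was not calculated for the substudy. The check therefore starts from the construction of the chart.

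**1. Between arms.** Let *n* be the subjects scanned in an arm and *m* the mean number of lesions per subject. The expected bar is *n* × *m*. With equal *m*, the ratio of bars is n(BKZ)/n(CZP), and *m* cancels.

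- 25 × 2/3 = 16.7, so the nearest splits are 17:8 and 16:9. The ratios are 17/8 = 2.13 and 16/9 = 1.78.
- With *m* = 3 (assumed) and 17:8, the bars are 51 and 24. With *m* = 10 they are 170 and 80.
- Divided by subjects, 51/17 = 3 and 24/8 = 3, a ratio of 1.0.
- No stratification by substudy is described. Treating the split as Binomial(25, 2/3), the 95% range runs from 12:13 to 21:4, that is from 12/13 = 0.92 to 21/4 = 5.25. The chance of a ratio of at least 1.5 is 82%.

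**2. Over time, the scan-only-if-positive rule.**

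- A subject negative at Baseline has no later scan, is outside the PET-PPS and adds 0 to every bar.
- A subject negative at Week 12 added 0 there and adds 0 at Week 48. The missing scan removes nothing from the total, but a new or recurrent lesion would go unseen.

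**3. Over time, withdrawal.** A lesion-positive subject scanned at Baseline and Week 12 is in the PET-PPS. If that subject leaves without a summarized Week 48 scan, the lesions stay in the first two bars and vanish from the third. With stable burden and a withdrawal fraction *w* unrelated to burden, the Week 48 bar is about (1 − *w*) of its value under full follow-up. For the 51 lesions above and *w* = 20%, this is 51 × 0.80 = 40.8.

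**4. Simulation of both rules together.** It assumed no treatment effect, stationary burden, mean lesions of 1, 3 or 8, persistence between visits of 0.5 or 0.9, and withdrawal after Week 12. With every PET-PPS subject counted at each visit, the Week 48/Week 12 ratio was 0.92 to 1.00. The plotted totals gave, for the bimekizumab arm:

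| Withdrawal (assumed) | Week 48 / Week 12 total |
|---|---|
| 0% | 0.87 to 1.00 |
| 10% | 0.79 to 0.89 |
| 20% | 0.71 to 0.80 |
| 30% | 0.61 to 0.70 |

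With a mean of 3 and 20% withdrawal, the Week 48 total was 75% to 79% of Baseline, against 95% to 99% with everyone counted. Lesions per scanned subject stayed level: 3.97 to 4.08 at persistence 0.5, and 4.01 to 4.04 at persistence 0.9. With no withdrawal, the scan rule alone took 0 to 5 percentage points off the Week 48/Baseline ratio; the largest effect was 0.76 against 0.81, at mean 1 and persistence 0.5. That gap consists of new or recurrent lesions that were not imaged.

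**The case against.** The strongest defence is that the correct numbers are already planned. SAP 8.3.6.2 specifies lesions per subject by visit and per-subject changes, and such a change exists only where both visits were scanned. The declared bone-formation variable is SUVauc, per lesion and as a subject maximum (SAP 2.2.1.3), not the lesion count. The substudy is exploratory and unpowered. The SAP is also silent on layout, so the number scanned may yet be printed under the bars. All of this stands. It limits the point to one misleading figure, and a reader should not infer that the substudy's conclusion rests on these charts.

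A second tempting inference is that the conditional follow-up scans make unscanned subjects look like improvement, or that the total falls whenever a scan is missing. The documents do not support either. Subjects skipped under that rule had no lesions to remove, and anyone with no evaluable post-Baseline scan is outside the PET-PPS and so out of the Baseline bar too. The fall arises only for lesion-positive PET-PPS subjects without a summarized scan at a visit, mainly those who withdraw before Week 48.

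A third is that the bars will stand at exactly 2:1. The realised split may differ, more so with PET-MRI subjects left out of the PET-CT summaries. That uncertainty does not rescue the chart, because readers then cannot mentally correct by a known factor.

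**Conclusion.** The point holds as a minor one about a single figure set. In expectation, equal arms give bars about two-fold apart (2.1 at 17:8, 1.8 at 16:9). Withdrawal lowers the Week 48 bar roughly in proportion: about 20% at an assumed 20% withdrawal, with no lesion resolved. If withdrawal differs between arms, so does the apparent improvement.

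The size rests on assumptions outside the documents: that 2:1 carries over to the substudy, the lesion means, their persistence, and withdrawal rates of 10% to 30% unrelated to lesion burden. The direction of both effects follows from the chart definition, the allocation ratio and the data-handling rules alone. No primary or secondary analysis is affected.

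**What to change.** In SAP 8.3.6.2, change the plotted variable to the mean number of PET-positive lesions per scanned subject, by arm and visit, and print the number scanned under each bar. In the figure, restrict comparison over time to subjects scanned at both visits. Keep total counts in the table only. Add a footnote that follow-up scans require a positive previous scan, because the per-scanned mean is conditional on that. In the low-burden simulation (mean 1, persistence 0.5, no withdrawal, no treatment effect) it moved from 2.00 to 1.75 to 1.90 across the three visits for this reason alone.

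The cost is one changed variable in one figure set. The per-subject counts are already derived for the planned summaries, and no new data are needed.
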